1.1. Clinical Study Title

진행성 핵상 마비 환자를 대상으로 GV1001 0.56 또는 1.12 mg/day 피하 투여 시 질환의 중증도 개선 효과와 안전성을 탐색하기 위한 다기관, 무작위 배정, 이중 눈가림, 위약 대조, 평행 설계, 전향적, 제2a상 임상시험

A Multi-center, Randomized, Double-blind, Placebo-controlled, Parallel design, Prospective, Phase IIa Exploratory Clinical Trial to evaluate the efficacy and safety of Subcutaneous Administration of GV1001 0.56 or 1.12 mg/day in Patients with Progressive Supranuclear Palsy

1.2. Phase

Phase 2a clinical study

2. Study Sites, Principal Investigators, and Sponsor

See [Appendix 1]. List of clinical trial participants and clinical trial pharmacists

3. Introduction

3.1. Background and Rationale

3.1.1. Overview of Progressive Supranuclear Palsy

Progressive supranuclear palsy (PSP) is a refractory neurodegenerative disease in which brain tissue shows 4-repeat (4R) tau protein aggregation and deposition, followed by progressive death of brain neurons, resulting in motor and cognitive impairment as well as emotional and behavioral regression. It shows rapid progression after the onset of symptoms and the patient dies within 5 to 8 years on average. As with most neurodegenerative diseases, it is difficult to confirm the exact prevalence or incidence of PSP because adequate population-based surveys have not been conducted. However, the prevalence is known to be 5 to 7 patients per 100,000 of the population¹⁻³⁾ because of the rare occurrence of the disease worldwide. It has been reported that the proportion of patients diagnosed with PSP among patients who visit hospitals with an onset of Parkinsonism is approximately 5 to 6%.^{4), 5)}

The pathologic mechanism of PSP is yet to be fully identified, but various mechanisms in the function and metabolism of tau protein in the brain nervous system are known to eventually result in aggregation of tau protein in cells and subsequent death of brain neurons that rapidly spreads into the brain nervous system, resulting in atrophy and degeneration of the brain.

The tau protein is a microtubule-associated protein (MAP) that stabilizes intracellular microtubules in the axon, a branch extending from the cell body of a neuron, and it mainly plays the role of regulating the assembly and migration of microtubules, spatial arrangement and composition, and transport through the axons of small organelles. The tau protein is finally synthesized as a protein after transcription and translation from a gene, and in this process, it undergoes modification processes such as phosphorylation, acetylation, and breaks to finally synthesize into a protein. In addition to PSP, neurodegenerative diseases characterized by the accumulation of tau protein such as Alzheimer's disease, corticobasal degeneration (CBD), Pick's disease, and frontotemporal dementia and parkinsonism linked to chromosome 17 (FTDP-17) are called tauopathies. The aforementioned protein synthesis process plays an important role in the pathophysiology that induces functional abnormalities of tau protein in tauopathies including PSP.

[figure not shown]

Figure 1 The *MAPT* locus, its pathological mutations, and tau protein isoforms

The tau protein is generated from the microtubule-associated protein tau (*MAPT*) gene (i.e., the tau gene) located at the q21 locus (17q21) of chromosome 17. The fact that mutations in the *MAPT* gene can cause FTDP-17 clearly supports the causal role of tauopathy in neurodegeneration.⁶ The tau gene consists of a total of 16 exons numbered from 0 to 14.⁷ Among them, according to the number of C-terminal (31 or 32 amino acids) amino acid repeats generated in exon 10 depending on the alternative splicing of exons 2, 3, and 10, it is classified as 3-repeat (3R) or 4-repeat (4R), respectively, if there are 3 or 4 repeated sequences. In addition, according to the number of insertion sequences of N-terminal (29 amino acids) present in exons 2 and 3, respectively, it is classified as 0N, 1N, or 2N if the number of insertion sequences is 0, 1, or 2. Summarizing the above, 6 tau isoforms are generated, ranging from 352 amino acids (shortest with 3R/0N) to 441 amino acids (longest with 4R/2N) in total. PSP is classified as a representative neurodegenerative disease of 4R tauopathy, and it can be seen that there are some common aspects with Alzheimer's disease in terms of pathophysiology[Figure 1].⁸

[figure not shown]

[figure not shown]
Figure 2 A schematic illustrating the central role of tau oligomers in neurodegeneration.

The tau monomers that are formed incorrectly during the modification process of protein synthesis are known to form tau oligomers, in which tau proteins are tangled and clumped together, and induce pathologies in brain neurons with the occurrence of hyperphosphorylation as well as cause apoptosis through various mechanisms, which ultimately results in neurodegenerative diseases.[Figure 2].⁹⁾

The latest strategy for the development of therapeutic agents based on the pathophysiology of tauopathies is as shown below[Table 1, Figure 3].⁸⁾ The post-translational modification strategy is a strategy applied in common with therapeutic agents being developed to target Alzheimer's disease, and the drugs are being developed as oral or parenteral administration drugs, rather than antibodies (passive immunity) or active immunity or gene therapeutic agents.

Table 1 Treatment development strategy for tauopathies

Disease	Astrocytes	Oligodendrocytes	Neurons	Tau 3R-4R-Mutant
PSP	Tuft astr Prot astr (Pretangles/tangles)	Coiled (Pretangles/tangles)	Pretangles/tangles	4R (a few prot astr 3R)
CBD	Astr sppd (Pretangles)	Coiled (Pretangles/tangles)	Pretangles/tangles	4R
Elderly tauopathy	Astr sppd (Pretangles)	—	Pretangles	4R
AGD	TsA (Pretangles/tangles)	Coiled (Pretangles/tangles)	Pretangles + AD*	4R
AD	TsA (when present) (Pretangles/tangles)	— (Pretangles/tangles)	Pretangles/tangles	4R/3R
PID	React astr (Pretangles)	Coiled (Pretangles/tangles)	Pick bodies Pretangles/tangles	3R (some fibrous astr 4R)
FTLD-tau/P301L	Astr prox gran incl (Pretangles)	Coiled + globular (Tangles)	Pretangles/tangles	4R mut
FTLD-tau/K317M	Astr tuft-li (Tangles)	GGI (Tangles)	Tangles	4R mut (a few glob incl 3R)
GGT	Tufted-like (Tangles)	GGI (Tangles)	Pretangles/rarely tangles	4R (a few GGIs 3R)

**Figure 3** Potential therapeutic targets for progressive supranuclear palsy

3.1.2. Information on Existing Therapies

Currently, it is not an exaggeration to say that therapies for patients with progressive supranuclear palsy are nonexistent. Disease-specific drugs have not been developed to date, and several central nervous system drugs are being used as popular treatments for neurological disorders. Levodopa (L-dopa), a precursor of dopamine, is often used in patients with early progressive supranuclear palsy, but only about 40% of patients show limited response to L-dopa, and the effect of the drug on improving neurological symptoms is known to be minimal. In addition, amantadine can show some mild symptomatic improvement effects as it shows dopaminergic effects as well as concurrent anticholinergic and anticholinergic effects. However, many other central nervous system drugs have been administered to try to improve the symptoms of patients with progressive supranuclear palsy, but there are no drugs that can delay or improve neurological disorders to date. Besides this, botulinum toxin injections are used symptomatically to treat blepharospasm, which is a focal dystonia, as well as the accompanying apraxia of eyelid opening.

Based on the pathological mechanisms of PSP that have been emerging recently, the development of various drug treatments and immunotherapies is being attempted in developed countries overseas, and there are several drugs

that are undergoing preclinical and clinical study Phases 1 and 2.

3.1.3. Background of Clinical Study (Rationale)

The clinical study results of the above drugs under development are still not promising, and there are no drugs that were able to successfully move on to a Phase 3 clinical study. In addition to PSP, new-concept clinical studies on new drugs for refractory neurodegenerative diseases have recently been conducted in North America and Europe, and drugs that have been approved by the U.S. Food and Drug Administration (US FDA) for some rare and refractory diseases and have begun sales are not realistically accessible for domestic patients because of their astronomical costs. Furthermore, since the pharmaceutical companies that developed the drugs are often overseas R&D companies, they do not have global sales lines, and thus are not applicable to domestic patients. Even if a drug is not a treatment for rare refractory diseases, various investigational drugs for relatively common neurodegenerative diseases such as Alzheimer's disease or Parkinson's disease take at least 5 to 10 years from the time of overseas sales in the US or Europe to their domestic introduction. Thus, waiting without appropriate treatment until the drugs developed overseas reach domestic sales is too dangerous for patients with neurodegenerative diseases whose first 3 years after diagnosis are crucial due to the rapid progression of disease. Therefore, even in the case of PSP, which is a representative refractory neurodegenerative disease, the development of treatments that meet the treatment standards and circumstances of domestic patients is absolutely necessary in terms of the cost and efficiency of Korean healthcare.

Summarizing the above, PSP is a neurodegenerative disease caused by tau protein abnormalities, and the pathophysiology is similar to Alzheimer's disease in that it is a tauopathy. Therefore, based on experimental evidence showing that GV1001 will improve neuronal viability and reduce the amount of aggregated tau, and the results of a preceding Phase 2 clinical study (KG6/2016) on Alzheimer's disease that was conducted domestically, there is a need to develop it as a treatment for PSP as well. PSP, which is 3 times faster than relatively common neurodegenerative diseases such as Alzheimer's disease or Parkinson's disease and is severely disabling, has no realistic treatment, and thus, the development of a treatment is desperately needed.

This clinical study has been planned in the form of a Phase 2 clinical study to scientifically verify the possibility of developing GV1001 as a treatment for PSP. Since GV1001 has already been studied in large-scale clinical studies on cancer diseases and Alzheimer's disease, and safety data have also been obtained from elderly patients with dementia, it is considered that the additional risks that occur in the process of developing it as a treatment for refractory neurodegenerative diseases such as PSP will be minimal. In addition, it is anticipated that it can become a breakthrough treatment if it is able to improve the symptoms that substantially lower the quality of life or partially reduce the speed of rapid progression that threatens life in PSP patients who have no existing treatments. Since the initial development process is conducted domestically, it has the conditions to be a very realistically useful drug that can be immediately applied to domestic patients if the clinical study is successful and product approval is obtained in the future. Therefore, there is an even more desperate need to conduct the clinical study domestically in Republic of Korea.

3.2. Mechanism of Action from Nonclinical Study Data of GV1001

- 
- No serious adverse events were reported for GV1001 in previously conducted nonclinical and clinical studies. In particular, safety in humans has been confirmed in various clinical studies on several target diseases in

which GV1001 was administered, with reports of only mild adverse events such as erythema at the site of administration and flu-like symptoms.

- Considering that GV1001 is a [REDACTED], *in vitro* and *in vivo* experiments were conducted under the assumption that the positive functions (i.e., cytoprotective effects, antioxidative effects, anti-inflammatory effects, etc.) [REDACTED] and these effects were confirmed as below. Therefore, it can be hypothesized that there will be therapeutic effects that can reduce apoptosis in neurodegenerative diseases such as Alzheimer's disease or PSP.
- First, the following were shown when experiments conducted in *in vitro* cell models and in transgenic animal models having *in vivo* Alzheimer etiologies¹³⁾ were examined.

1) [REDACTED]

[REDACTED]

[REDACTED]

Figure 4 [REDACTED]

2) [REDACTED]

[REDACTED]

[REDACTED]

Figure 5 [REDACTED]

3) [REDACTED]

[REDACTED]

Figure 6 [REDACTED]

4) [REDACTED]

Figure 7 [REDACTED]

5) [REDACTED]

Figure 8

6)

**Figure 9**

- In addition, the following were shown when the results of animal experiments conducted on a transgenic animal model (██████████) with a tau etiology showing progressive supranuclear palsy disease were examined.

1)

**Figure 10**

2)

Figure 11

3)

Figure 12

4)

1) [REDACTED]

2) [REDACTED]

3)

4)

Figure 13

4)

1)

2)

**Figure 14**

Summarizing these experiment results, it can be inferred that GV1001, through various mechanisms, is able to effectively inhibit apoptosis caused by the main pathological mechanism of neuronal degeneration. Furthermore, it can be summarized that the drug will show efficacy in PSP because the potential mechanisms reduce reactive oxygen species, prevent apoptosis, inhibit formation of total tau and tau oligomers, decrease the amount of aggregated tau protein, and promote spontaneous neurogenesis.

3.3. Results of Past Clinical Studies

[figure not shown]
To date, GV1001 has been applied to patients with a variety of diseases through clinical studies and individual therapeutic use approval procedures. For PSP, the target disease of this clinical study, GV1001 was administered for

The PSP-rating scale (PSP-RS)¹⁴ is a measure of efficacy validated as a method of quantitatively evaluating the neurological status of patients with PSP.

**Figure 15** [Redacted content block]
[Redacted content block]

For reference, in a large-scale Phase 2/3 Davunetide clinical study¹⁶, the progression of disease in PSP patients who participated increased by 6.8 points on average after 6 months of treatment contrary to expectations, and thus, it was shown that the natural progression of worsening symptoms could not be changed.

**Figure 16** PSP-RS change in PSP patients administered Davunetide or placebo in clinical trial of NCT01110720

3.4. Rationale for Dose Setting

The dose of the investigational product to be used in this clinical study was determined by the process of deriving the maximum recommended starting dose for human clinical studies on new drugs.

[Redacted content block]

Summarizing the above results, the safe starting dose for the PSP clinical study was 0.56 mg/day ([REDACTED]), and the second dose was determined as 1.12 mg/day ([REDACTED]).

In addition, at the previously implemented doses of GV1001 0.56 to 1.12 mg/day used in patients approved for therapeutic use of the drug, no significant adverse events were reported, similar to other clinical studies, and significant clinical improvements were shown in the change of the PSP-RS score. Moreover, since results of improvement could be observed in other clinical symptoms, it was determined that the dose of 0.56 to 1.12 mg/day is appropriate in this clinical study.

Based on the above considerations, this clinical study intends to conduct a final validation on the efficacy and safety of two doses of GV1001 0.56 mg/day and 1.12 mg/day.

4. Study Objectives

4.1. Primary Objective

To explore the efficacy and evaluate the safety of GV1001 0.56 mg/day or 1.12 mg/day administered for 24 weeks on the severity of disease in patients with progressive supranuclear palsy.

4.2. Secondary Objectives

To collect source data to determine the possibility of progression to the next stage of development and to subsequent clinical studies by analyzing the clinical and biological parameters associated with the treatment response and safety information of 2 dose levels of GV1001, 0.56 mg/day or 1.12 mg/day, in patients with progressive supranuclear palsy.

5. Clinical Study Population

5.1. Target Number of Subjects

Total number of subjects: 75 subjects (75 subjects in total with 25 subjects per group considering a dropout rate of 20%)

	Study Group 1	Study Group 2	Control Group	Total Number of Subjects
Number of Subjects	20	20	20	60
Number of Subjects Considering Dropout (20%)	25	25	25	75

5.2. Target Patients

Progressive supranuclear palsy

5.3. Inclusion Criteria

- 1) Patients aged \geq 41 years to \leq 85 years
- 2) Patients clinically diagnosed with a probable PSP (Richardson type [PSP-RS] or parkinsonian type [PSP-p]) by the diagnostic criteria for PSP developed by the International Parkinson and Movement Disorders Society Task Force
- 3) In the case of the PSP-RS type, patients with clearly identified supranuclear ophthalmoplegia (SOP) according to the judgment of the investigator (e.g., the sum of scores in the ocular motor part of the PSP-rating scale must be \geq 5 points or the downgaze [voluntary downward command movement] score must be \geq 2 points). In the case of the PSP-p type, patients identified as having shown little or no response to previous administration of levodopa according to the judgment of the investigator during the course of treatment
- 4) Patients who had been taking a stable dose of a neurological drug for at least 1 month prior to screening without changes in the dose
- 5) Patients who are able to walk 3 meters or more independently or with assistive devices
- 6) Patients with at least 15 points on the Korean Mini-Mental State Examination (K-MMSE) at the screening visit (however, the results of a test performed at the study site within 2 weeks prior to the screening visit may be used if available)
- 7) Patients who have a guardian who can accompany the patient at all visits according to the schedule of this clinical study, and who is able to supervise the subject's compliance with the test and examination procedures performed at the visits and provide information on the subject's indication, and whose guardians have provided a written consent for participation in the clinical study
- 8) Patients and/or their representatives who have voluntarily provided a written consent for participation in this clinical study

5.4. Exclusion Criteria

- 1) Patients who fall under any of the following based on the CT/MRI scan results and neurological examinations performed within 12 months of screening or at screening
 - Presence of structural lesions (vascular, neoplastic, inflammatory, infectious, demyelinating, etc.) that can clinically affect the patient's symptoms of progressive supranuclear palsy on brain CT or MRI
 - Suspected concurrent onset of central nervous system diseases* other than progressive supranuclear palsy that, according to clinical judgment, can cause parkinsonism
 - *Dementia or motor disorders due to vascular brain disease, subdural hematoma, normal pressure hydrocephalus, brain tumor, Alzheimer's disease, multiple system atrophy, Creutzfeldt-Jakob disease, etc.
- 2) Patients with a history of known or suspected seizures (including febrile seizure)
- 3) Patients with a recent unexplained loss of consciousness within 3 months prior to screening or a history of significant head trauma with loss of consciousness

- 4) Patients with acute or unstable cardiovascular disease, uncontrolled hypertension (exceeding 160/100 mmHg), uncontrolled diabetes (insulin-dependent or HbA1c >8%), or any other medical condition that can interfere with completing the clinical study
- 5) Patients with hypersensitivity reactions to the ingredients of the investigational product
- 6) Patients with a history of cancer within 5 years prior to screening (however, nonmetastatic basal cell carcinoma of the skin, squamous cell carcinoma of the skin, carcinoma in situ of the cervix, or nonprogressive prostate cancer are allowed)
- 7) Patients with abnormal renal function (creatinine clearance [CLcr] < 30 mL/min on screening test)
- 8) Patients with severe liver function abnormalities (ALT or AST is \geq 2.5 times the upper limit of normal on screening test)
- 9) Patients weighing \leq 35 kg
- 10) The woman of childbearing potential and male subjects who do not agree to contraception using medically acceptable methods (surgical sterilization, intrauterine contraceptive device, tubal ligation, double-barrier methods [combined use of barrier methods such as male condoms, female condoms, cervical caps, contraceptive diaphragms, and contraceptive sponges]), a single-barrier method with spermicide, and complete abstinence) during the clinical study and up to 90 days after the end (discontinuation) of their participation in the clinical study.
However, women who have gone through menopause* or women or men who have undergone surgical sterilization (vasectomy, bilateral tubal ligation, etc.) before participating in the clinical study can participate even if they do not agree to contraception.
* In this clinical study, menopause is defined as one or more of the following
 - (1) Female subjects aged \geq 55 years who have had amenorrhea for more than 1 year
 - (2) Female subjects aged \geq 41 years to $<$ 55 years who have had amenorrhea for more than 1 year and have a serum follicle stimulating hormone (FSH) level \geq 30 mIU/mL
 - (3) In case of artificial menopause caused by bilateral oophorectomy
- 11) Pregnant or breastfeeding women
- 12) Patients who participated in another clinical study within 4 weeks prior to screening and were administered investigational products or were applied investigational medical devices
- 13) Patients who were administered the study drug (GV1001) of this clinical study within 12 months prior to screening
- 14) Patients who participated in a clinical study for progressive supranuclear palsy within 6 months prior to screening
- 15) Other patients judged by the investigator as ineligible to participate in this clinical study

5.5. Dropping Out

5.5.1. Definition

Subjects who have been randomized but are unable to participate for the entire duration of the clinical study for any reason will be classified as dropouts. Subjects may discontinue the study at any time at their own request, or may be dropped out at any time at the discretion of the investigator or sponsor for safety, behavioral, or administrative reasons.

The investigator shall ask the subject regarding the reason for dropping out, and request the subject to visit the study site for the last time to undergo the tests performed at Visit 16. If applicable, every effort shall be made to follow up on the subject with regard to unresolved adverse events.

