6.2 Windowing Conventions

The results of efficacy assessments performed after randomization in this study will include not only regular visits, but also early termination/withdrawal visits and unscheduled visits, and measurements from the visit within the visit window will be used for the analysis.

Visit	Actual Point	Visit Window	Analysis Window Valid Relative Range*
Visit 1 (Screening)	~ - 4 Week	-	
Visit 2 (Baseline)	Week 1	-	1
Visit 3	Week 2	± 3 Days	5~11 days
Visit 4	Week 3	± 3 Days	12~18 days
Visit 5	Week 4	± 3 Days	19~25 days
Visit 6	Week 6	± 5 Days	31~41 days
Visit 7	Week 8	± 5 Days	45~55 days
Visit 8	Week 10	± 5 Days	59~69 days

Visit	Actual Point	Visit Window	Analysis Window Valid Relative Range*
Visit 9	Week 12	± 5 Days	73~83 days
Visit 10	Week 14	± 5 Days	87~97 days
Visit 11	Week 16	± 5 Days	101~111 days
Visit 12	Week 18	± 5 Days	115~125 days
Visit 13	Week 20	± 5 Days	129~139 days
Visit 14	Week 22	± 5 Days	143~153 days
Visit 15 (EOT)	Week 24	± 5 Days	157~167 days
Visit 16	Week 26	± 5 Days	171~181 days
Visit 17 (EOS)	Week 28	± 5 Days	185~195 days

* If a violation of the drug administration schedule occurs, the analysis window will be modified as the process in the protocol 5.5.2.

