5.5.4. Handling of Dropouts and Protocol Violations

Any of these situations shall be documented in the subjects' case report forms and source documents. For subjects who have been dropped out, the relevant reason will be recorded in the Clinical Trial Completion section of the case report form. Even if a subject has been dropped out, the results of previous tests shall be included in the analysis.

In the case of a subject who has been dropped out because of an adverse event, the subject will be followed up

until the subject recovers to the state prior to investigational product administration or to the baseline, or until the principal investigator can determine that the adverse event has normalized.

After randomization, subjects who discontinue participating in the clinical study or drop out, regardless of the reason, shall not be replaced.

6. Details of Clinical Study Design

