6.1. Clinical Study Duration

Approximately 24 months from the approval date of the Ministry of Food and Drug Safety and the Institutional Review Board (IRB) of the study site

Subject enrollment duration: Approximately 10 months

- Duration of participation for each subject: Approximately 8 months (32 weeks in total—4 weeks for screening, 24 weeks for treatment, 4 weeks for safety follow-up)
- Data management, statistical analysis, and completion of clinical study report after the end of study: Approximately 6 months

However, the planned duration of study may be extended or shortened depending on the speed of subject enrollment, changes in the procedures after the end of study, etc.

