10.2.10. Visit 17 (End-of-Study Visit, Week 28 ± 5 days)

This is the study termination visit, which will be conducted over the telephone.

- Changes in the prior/concomitant drug administration history will be checked compared with the previous visit.
- The occurrence of adverse events since the previous visit and their details will be investigated.

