10.5.2. Reporting of Adverse Events

- Adverse events will be collected during the clinical study from the time point after investigational product administration and up to the final visit. All medical events that occur prior to investigational product administration will be recorded as medical history.
- Adverse events shall be reported by including the name of the adverse event, duration (start date and disappearance date), severity, causal relationship to the investigational product, actions taken for the investigational product, outcome, corrective treatment for the adverse event, and whether the event is a serious adverse event.
- When recording an adverse event, the investigator shall use a comprehensive diagnosis or symptom using standard medical terminology rather than recording each symptom or sign.
- Adverse events that occur during the clinical study shall be followed up until they disappear, show stable outcomes, or the subject is lost to follow-up.
- Adverse events that occur after the end of the clinical study shall be reported only if they are serious and related to the investigational product.

1) Severity Assessment

The investigator will assess the severity of adverse events and serious adverse events by referring to the criteria described below.

Mild	The event causes minimal discomfort without interfering with the subject's normal daily life (function), and it can be easily tolerated by the subject.
Moderate	The event causes discomfort that significantly interferes with the subject's normal daily life (function).

Severe The event makes the subject's normal daily life (function) impossible.

Activities of daily living are defined below.

: All activities that occur in daily life to take care of one's own body (e.g., bathing, dressing and undressing, eating, taking medications, hygiene, and personal care)

An adverse event or serious adverse event can both be evaluated as severe according to the definition above, and one should not be confused for the other since a severe adverse event does not necessarily correspond to a serious adverse event.

2) Causality Assessment

The investigator will assess the causal relationship between an adverse event and the investigational product by referring to the criteria described below. If it is assessed as unlikely, it can be determined as "no causal relationship" (non-ADR). If it is assessed as other items, it will be determined that there is a causal relationship (ADR).

- ① Certain

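### The protocol sets no minimum time after the last dose for seeking new adverse events in subjects who drop out, so their observation for harms can be shorter than in completers

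*Combined protocol and SAP*

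**What the plan says.** **Dropouts.** Protocol 5.5.1 has the investigator "request the subject to visit the study site for the last time to undergo the tests performed at Visit 16". It then adds that, where applicable, "every effort shall be made to follow up on the subject with regard to unresolved adverse events". Section 5.5.4 adds: "In the case of a subject who has been dropped out because of an adverse event, the subject will be followed up", until recovery or until the event is judged to have normalised. Neither section gives a time from the last dose or mentions a later enquiry about new events.

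**Collection period.** Section 10.5.2 states: "Adverse events will be collected during the clinical study from the time point after investigational product administration and up to the final visit". Section 10.5.3 sets the same end for SAEs. Both add a rule for later events: "Adverse events that occur after the end of the clinical study shall be reported only if they are serious and related to the investigational product".

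**Completers.** Section 6.1 splits each subject's participation into "4 weeks for screening, 24 weeks for treatment, 4 weeks for safety follow-up". The last dose is at Visit 15, which SAP 6.2 lists as "Visit 15 (EOT) Week 24 ± 5 Days 157~167 days". Visit 17 is a telephone contact at Week 28, at which "The occurrence of adverse events since the previous visit and their details will be investigated" (10.2.10).

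**Text that points elsewhere.** Section 7.1 deems the study completed at Visit 16 and provides follow-up to Week 28 only where an AE is unresolved. Section 10.2.9 includes arranging the telephone visit among the Visit 16 items.

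**The concern.** Evaluating safety is part of the primary objective. SAP 10.2.2.1 reports AE and SAE incidence by arm as crude percentages, with a chi-square or Fisher comparison of AE incidence and no adjustment for time observed. The definition of a treatment-emergent event in SAP 10.2.1 has no end date. How long each subject is asked about new events therefore feeds directly into the numerator.

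If a dropout's final visit is the exit visit, and that visit can fall on a dosing day, a new event in the following days has no required route into the database. AEs are one of the listed reasons for dropping out (5.5.2), so the subjects with the shortest required observation may include some whom a safety evaluation most needs to follow. An arm that loses more subjects would also have more unobserved post-dose time.

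**Working it through.** **Plan's own figures.** Dropout inflation: 20 / (1 − 0.20) = 25 per arm, 75 in total, as stated in 11.4. Study-day centres from SAP 6.2, (week − 1) × 7 + 1: Visit 15 = 162, Visit 16 = 176, Visit 17 = 190. Visit 17 minus Visit 15 = 28 days, which matches the 4 weeks in 6.1.

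**Last dose to last required enquiry about new events**

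| Subject and reading | Nominal | Range with windows |
|---|---|---|
| Completer, Visit 17 applies (6.1, 10.2.10) | 190 − 162 = 28 days | 185 − 167 = 18 to 195 − 157 = 38 |
| Completer, 7.1 governs and no AE is unresolved | 176 − 162 = 14 days | 171 − 167 = 4 to 181 − 157 = 24 |
| Dropout, exit visit is final | not set | from 0 days |

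The 0 is inferred from the absence of a minimum interval. The exposure formula in SAP 10.1.1 is consistent with it, since it accepts a discontinuation date equal to the last dosing date.

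If the Week 28 call does apply to dropouts, the interval is still not tied to the last dose. A subject last dosed at Visit 5 (Week 4, Day 22) would be called 190 − 22 = 168 days later. Neither reading gives dropouts and completers the same window.

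**Size.** Dropouts: 0.20 × 75 = 15, or 5 per arm if spread evenly. Intended post-dose time at 28 days each: 75 × 28 = 2,100 subject-days. Time not required if all 15 exit on a dosing day: 15 × 28 = 420 (20%). If all exit 7 days after the last dose: 15 × 21 = 315 (15%). At 14 days: 15 × 14 = 210 (10%).

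**Effect on incidence (illustration).** Let q be the chance that a dropout has a first countable AE in the lost 28 days. The documents give no value, so I assume 5% to 40%.

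- Five dropouts per arm, all exiting on a dosing day: 5 × 0.05 = 0.25 to 5 × 0.40 = 2 subjects per arm missed. Over 25 that is 1 to 8 percentage points, with a ceiling of 5/25 = 20 points.
- With the same q and equal dropout, the shortfall is the same in each arm and cancels in the difference.
- With 8 dropouts in one arm and 2 in the other (assumed), the difference is shifted by 6 × q / 25 = 1.2 to 9.6 points.

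**The case against.** The strongest reply is that the gap is one of wording. Section 5.5.1 speaks of the last visit to the site, and Visit 17 is a telephone contact, so the one does not exclude the other. The Visit 16 list includes arranging that call, and 6.1 gives 4 weeks of safety follow-up to each subject without exempting dropouts. This stands as far as it goes: a reader might infer that AE collection stops at exit as a stated rule, and the documents do not say so. But 5.5.1 brings in only the tests of Visit 16, SAP 6.3 treats an early termination visit that comes last as the final visit for safety summaries, and nothing requires a later enquiry about new events. The protocol leaves the question open.

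Three further inferences are tempting and not supported.

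- *Harms are under-counted in those most likely to have them.* AEs are one reason among several for dropout. The AE that led to exit is already in the numerator and is followed further. Only new-onset events after exit are exposed.
- *The comparison is biased toward no excess harm.* This needs unequal dropout or unequal event rates, and the documents give neither.
- *An SAE shortly after a dropout's exit is reportable only if related.* That limit applies after the end of the study, which 7.1 defines for the whole study as the last enrolled subject's termination visit. The text does not equate that with one subject's exit. It leaves the time between the two without a clear rule.

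It is also fair that the 28-day comparator is disputed by 7.1, that many exits will not fall on a dosing day, and that a call cannot reach subjects who are lost or refuse contact. Nor does it restore on-treatment time lost by leaving early.

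**Conclusion.** The point holds as a gap in the plan: no minimum time after the last dose is set for seeking new AEs or SAEs in dropouts, while completers have a nominal 28 days, or 14 if 7.1 governs. About 15 of 75 subjects are affected at the planned 20% dropout. The 420 of 2,100 subject-days is an upper limit that assumes every dropout exits on a dosing day and could have been reached. The 1 to 8 point shortfall per arm rests on that same timing and on the assumed 5% to 40% event rate. Whether the arms would be affected differently cannot be judged from the documents. It should be corrected because the remedy is small, safety is part of the primary objective, and the sections on follow-up do not agree with one another.

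**What to change.** - **Protocol 5.5.1 and 10.2.10:** apply the existing Visit 17 telephone AE enquiry to every subject who received at least one dose and leaves early, unless contact is refused. Time it from the last dose, using the 4-week follow-up period already in 6.1.
- **Protocol 10.5.2 and 10.5.3:** define the end of AE and SAE collection for each subject as the later of the exit visit and that call.
- **Reconcile 5.5.1, 6.1, 7.1, 10.2.9 and 10.2.10,** so that it is clear who receives the Week 28 contact and whether it depends on an unresolved AE.
- **SAP 10.2.1:** give the treatment-emergent definition an end expressed in days from the last dose, the same for completers and dropouts.

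The cost is about 15 telephone calls on an existing form, some wording in both documents, and slightly later data completion for late dropouts.
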